## 7.2.3. Rationale for the Study Population

The subject population includes males and females ranging from 6 to 12 years of age (at time of consent/assent and at Baseline in the core study SEP360-202); and in concert with standard practice guidelines, will be required to have a diagnosis of ADHD established by a comprehensive psychiatric evaluation that reviewed Diagnostic and Statistical Manual for Mental Disorders Fifth Edition (DSM-5) criteria for a primary diagnosis of ADHD (inattentive, hyperactive, or combined presentation); diagnosis was confirmed at screening for the core study using the Schedule for Affective Disorders and Schizophrenia for School-Age Children Present and Lifetime Version (K-SADS-PL).

## 7.2.4. Rationale for the Endpoints

The safety assessments and their timing are considered appropriate to assess the long-term safety of dasotraline, taking into account known pharmacology and adverse events based on previous studies. The symptom, functional, and quality of life assessments were selected to address the potential effectiveness of dasotraline on these parameters.

#### 7.2.5. Prevention of Missing Data

In an effort to minimize the number of subjects who are terminated from the study prior to study completion, the following study design and conduct elements are implemented; (i) allowance of dose adjustment throughout the study based on effectiveness and tolerability, (ii) study site

contact with subjects between the monthly study visits during the treatment period, (iii) site training on the importance of continued follow-up and on the informed consent process, ensuring subject/parent/legal guardian understand the commitment they are making, including the intent to complete the trial, and (iv) data monitoring for adherence during the study.

## 8. SELECTION OF SUBJECTS

Eligibility criteria will be assessed at the open-label (OL) Baseline visit (Week 6 in the core study). Assessments performed as part of the Week 6 visit in the core study do not need to be repeated.

# 8.1. Subject Inclusion Criteria

- 1. At least one of the subject's parents/legal guardians must give written informed consent, including privacy authorization, prior to study participation. The subject will complete an informed assent prior to study participation.
- 2. Subject and subject's parent/legal guardian are judged by the investigator to be willing and able to comply with the study procedures and visit schedules.
- 3. Subject has completed all required assessments for Week 6 of the core study.
- 4. Subject has not taken any medication other than the study drug for the purpose of controlling ADHD symptoms during the core study.
- 5. Subject, if female, must not be pregnant or breastfeeding.
- 6. Female subject:
  - must be unable to become pregnant (eg, premenarchal, surgically sterile, etc);
     -OR-
  - practice true abstinence (consistent with lifestyle) and must agree to remain abstinent from signing informed consent/assent to at least 14 days after the last dose of study drug has been taken;

-OR-

- is sexually active and willing to use a medically effective method of birth control (see Appendix IV, Section 23) from signing informed consent/assent to at least 14 days after the last dose of study drug has been taken.
- 7. Male subject must be willing to remain sexually abstinent (consistent with lifestyle) or use an effective method of birth control, (Appendix IV, Section 23), from signing informed consent/assent to at least 14 days after the last dose of study drug has been taken.
- 8. Any subject whose weight is < 21 kg at the OL Baseline visit should be discussed with the medical monitor prior to enrollment.
- 9. Subject and subject's parent/legal guardian must be able to fully comprehend the informed consent/assent form (as applicable), understand all study procedures, and be able to communicate satisfactorily with the Investigator and study coordinator.

# 8.2. Subject Exclusion Criteria

- 1. Subject is considered by the investigator to be at imminent risk of suicide, injury to self or to others, or damage to property.
- 2. Subject answers "yes" to "Suicidal Ideation" item 4 (active suicidal ideation with some intent to act, without specific plan) or item 5 (active suicidal ideation with specific plan and intent) for any lifetime history on the C SSRS Children's "Since Last Visit" assessment at OL Baseline.
- 3. Subject has a clinically significant abnormality including physical examination, vital signs, ECG, or laboratory tests that the investigator in consultation with the medical monitor considers to be inappropriate to allow participation in the study.
- 4. Subject has a positive urine drug screen (UDS) or breath alcohol test at OL Baseline.
- 5. Subject or parents/legal guardian has commitments during the study that would interfere with attending study visits.
- 6. Subject is at high risk of non-compliance in the investigator's opinion.

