#### Exclusion Criteria:

- 1. Subject is considered by the investigator to be at imminent risk of suicide, injury to self or to others, or damage to property.
- 2. Subject answers "yes" to "Suicidal Ideation" item 4 (active suicidal ideation with some intent to act, without specific plan) or item 5 (active suicidal ideation with specific plan and intent) for any lifetime history on the C-SSRS Children's "Since Last Visit" assessment at OL

Baseline.

- 3. Subject has a clinically significant abnormality including physical examination, vital signs, ECG, or laboratory tests that the investigator in consultation with the medical monitor considers to be inappropriate to allow participation in the study.
- 4. Subject has a positive urine drug screen (UDS) or breath alcohol test at OL Baseline.
- 5. Subject or parents/legal guardian has commitments during the study that would interfere with attending study visits.
- 6. Subject is at high risk of non-compliance in the investigator's opinion.

**Investigational Product, Dosage and Mode of Administration:** Dasotraline 2, 4, and 6 mg capsules for oral administration will be supplied. One capsule of study drug will be taken once daily for 26 weeks (Day 1 through Day 182), at approximately the same time each morning without regard for food including on the days when clinic visits occur. If morning dosing is not tolerated then dosing may be at another time of day with prior medical monitor approval; however, if there is a time of day dosing change, subjects should administer study drug at the same time of day for the remainder of the study. Dose schedule and adjustment are described under Study Design.

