Children's Sleep Habits Questionnaire (CSHQ)	X (carried over)	X	X	X	X	X	X	X	X	X			
Weiss Functional Impairment Rating Scale – Parent Report (WFIRS-P)	X (carried over)						X			X			
Physician Withdrawal Checklist (PWC) j										X			X
Discontinuation-Emergent Signs and Symptoms (DESS) Scale j										X	X	X	X

Table 2: Schedule of Assessments (Continued)

	OL Baseline a				T	reatment I	Period				Wi	thdrawal Pe	eriod
Visit	1E	2E	3E	4E	5E	6E	7 E	8E	9E	10E/ET	11E Call	12E Call	13E/EOS
Week		Week 1	Week 2	Week 4	Week 6	Week 10	Week 14	Week 18	Week 22	Week 26 b	Week 27 b	Week 28 b	Week 29 b
Day	Day 0	Day 7 ± 3	Day 14 ± 3	Day 28 ± 3	Day 42 ± 3	Day 70 ± 3	Day 98 ± 3	Day 126 ± 3	Day 154 ± 3	Day 182 ± 3	Day 189 ± 3	Day 196 ± 3	Day 203 ± 7
Hematology/Chemistry	X (carried over)						X			X			X
Thyroid panel f	X (carried over)						X			X			X
Lipid panel g	X (carried over)						X			X			X
Sex hormone tests h	X (carried over)						X			X			X
Serum β-hCG (in females) i	X (carried over)												X
Urinalysis	X (carried over)						X			X			X
Urine drug screen	X (carried over)		X		X	X	X	X	X	X			X
Urine β-hCG (in females) i					X	X	X	X	X	X			
Breath alcohol test	X (carried over)						X						X

Abbreviations: β-hCG = beta-human chorionic gonadotropin, EOS = end of study, ET = early termination, OL = open label

Footnotes are continued on the next page.

<sup>a Week 6 in core study. Baseline assessments indicated as "carried over" are performed as part of Week 6 visit in the core study (with the exception of medical and psychiatric history from screening in the core study) and do not need to be repeated; the data will be duplicated from Week 6 visit in the core study.

<sup>b Subjects who discontinue from the study prior to completion will be asked to return to the site and complete the ET assessments within 3 days of discontinuation and complete all withdrawal period assessments (calls) and EOS visit.

- c Subjects will take the first dose of study drug in this study on Day 1, the morning following the baseline visit; there will be no break in study drug treatment between the core study and this extension study. All study drug will be administered by the subject in the morning. Subjects wishing to take study drug at an alternate time of day require investigator and medical monitor approval.

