#### 11.3.6. Safety Scales

#### Columbia Suicide Severity Rating Scale (C-SSRS) Children's Assessment

The C-SSRS (Posner-2007) is a tool designed to systematically assess and track suicidal AEs (suicidal behavior and suicidal ideation) throughout the study. The strength of this suicide classification system is in its ability to comprehensively identify suicidal events while limiting the over identification of suicidal behavior. The scale takes approximately 5 minutes to administer. The C-SSRS will be administered by a trained rater at the site.

For all visits the "Since Last Visit" version of the C-SSRS will be administered.

Subjects who have significant findings for suicidal ideation upon completion of the C-SSRS at any time during the study must be referred to the investigator for follow-up evaluation.

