# 11.4. Study Visits and Assessments

#### 11.4.1. Open-label Baseline: Visit 1E (Day 0)

Subjects will be evaluated at the Open-label Baseline Visit to determine their eligibility to enroll in the study. The following study-related procedures will be performed at Open-label Baseline in the following order:

- Obtain informed consent/assent
- Review inclusion/exclusion criteria
- Dispense study drug

The following study-related procedures will be carried over from the core study Week 6 visit and do not need to be performed for the Open-label Baseline visit:

- Medical and psychiatric histories
- Physical and neurological examinations
- Concomitant medications
- Vital signs, height, weight, and BMI
- AEs
- ECG
- Tanner Staging
- C-SSRS, CGI-S, ADHD-RS-IV HV, Conners 3-P, CSHQ
- WFIRS-P
- Clinical laboratories (hematology, chemistry, lipid panel, thyroid panel, sex hormone tests, urinalysis), UDS, and serum pregnancy test for females of child bearing potential
- Breath alcohol test

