12.9. Columbia-Suicide Severity Rating Scale (C-SSRS)

The Columbia-Suicide Severity Rating Scale (C-SSRS) is a questionnaire used for suicide assessment that evaluates suicidal ideation and behavior.

This study will utilize the “Since Last Visit” version of the C-SSRS at each visit.

Subjects will be placed into categories for suicidal ideation and for suicidal behavior based on their responses to various questions.

The Suicidal Ideation categories will be determined as follows by examining the response to the 5 questions under Suicidal Ideation.

Type	Section
Suicidal Ideation	
(0) None - if response is No to Questions 1 and 2
 
(1) Wish to be Dead - if response to Question 1 is Yes and responses to Questions 2-5 are No.
 
(2) Non-Specific Active Suicidal Thoughts - if response to Question 2 is Yes and response to Questions 3-5 are No.
 
(3) Active Suicidal Ideation with Any Methods (Not Plan) without Intent to Act - if response to question 3 is Yes and response to questions 4 and 5 are No.
 
(4) Active Suicidal Ideation with Some Intent to Act, without Specific Plan - if response to Question 4 is Yes and response to Question 5 is No.
 
(5) Active Suicidal Ideation with Specific Plan and Intent - if response to Question 5 is Yes.

For suicidal behavior, the following categories will be used. The categories will be determined based on the response to the questions under Suicidal Behavior.

Type	Section
Suicidal Behavior	
 • Preparatory Acts or Behavior - if response to Preparatory Acts and Behavior is Yes and responses to Actual Attempt, Interrupted Attempt, and Aborted Attempt are No • Aborted Attempt - if response to Aborted Attempt is Yes and responses to Actual Attempt and Interrupted Attempt are No. • Interrupted Attempt - if response to Interrupted Attempt is Yes and response to Actual Attempt is No. • Actual Attempt - if response to Actual Attempt is Yes. • None - if responses to all the above 4 questions are No.

The frequency and percentage by DB treatment and overall, and visit will be summarized for all C-SSRS responses.

Frequency and severity of suicidality using the C-SSRS will be summarized, using a shift table to examine changes in C-SSRS Scores from baseline compared to the worst (highest) category during the treatment period and visit, by DB treatment and overall.

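### Exclusion 2 sets a lifetime rule for C-SSRS ideation items 4 and 5 but reads it from the carried-over core Week 6 Since Last Visit form, so a report at an earlier core visit can pass the named check

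*Protocol*

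**What the plan says.** Exclusion 2 appears twice in the Protocol, in the Synopsis ("for any lifetime history on the C-SSRS") and in section 8.2 ("for any lifetime history on the C SSRS"). Both versions concern ideation item 4 (active ideation with some intent but no specific plan) and item 5 (active ideation with plan and intent). Both take the answer from the Children's Since Last Visit form at OL Baseline.

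The documents say where that form comes from:

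- Protocol section 8: "Assessments performed as part of the Week 6 visit in the core study do not need to be repeated".
- Protocol Table 2, footnote a: carried-over baseline assessments "do not need to be repeated; the data will be duplicated from Week 6 visit in the core study". The C-SSRS row is marked as carried over.
- Protocol section 11.4.1 lists the C-SSRS among procedures "carried over from the core study Week 6 visit and do not need to be performed" at OL Baseline.

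They also say which version is used. Under Protocol section 11.3.6, at every visit the Since Last Visit "version of the C-SSRS will be administered". SAP section 12.9 likewise specifies the Since Last Visit "version of the C-SSRS at each visit". Neither document schedules a lifetime version in this study.

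**The concern.** A form that asks about the time since the last visit cannot answer a lifetime question. A site that follows exclusion 2 literally looks at the Week 6 form, sees no to items 4 and 5, and enrols the child. That child may have reported ideation with intent at an earlier core visit. Nothing in the criterion sends the site to the earlier forms.

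The issue is the safety of children aged 6 to 12 at core entry who are starting 26 weeks of open-label treatment. Some were on placebo in the core study, and the permitted maximum of 6 mg/day exceeds the core doses of 2 and 4 mg/day (SAP section 6.1). Exclusion 2 is also the only place in these documents where a yes to item 4 or 5 by itself forces a decision. During the study, significant ideation leads to referral to the investigator, and discontinuation under section 13.1 rests on the investigator's opinion. With about 40 centers, the conflict may also be settled differently from site to site.

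**Working it through.** No arithmetic beyond counting applies, and the plan states no figure to reproduce. The check sets the provisions side by side.

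1. **Scope stated in exclusion 2:** lifetime, items 4 and 5.
2. **Source named in exclusion 2:** the Since Last Visit form at OL Baseline.
3. **Identity of that form:** the core Week 6 form, duplicated (Table 2 footnote a; sections 8 and 11.4.1). Forms consulted: 1.
4. **Period covered:** one between-assessment interval. This is inferred from the form's title; neither Protocol section 11.3.6 nor SAP section 12.9 defines the recall period. The interval's length depends on the core visit schedule, which the documents do not give.
5. **Other sources named for exclusion 2:** none. Where the Protocol wants a look-back over the core study it says so: inclusion 4 asks about ADHD medication taken during that study. Exclusion 2 has no such wording.

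Now take a child who answered yes to item 4 at a core assessment before the last interval and no at Week 6. This assumes that the core study collected the C-SSRS at least once before Week 6.

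| Reading of exclusion 2 | Result for this child |
|---|---|
| The lifetime words govern | Excluded |
| The named form governs | Not flagged |

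The two halves of one criterion give opposite answers.

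The safeguards elsewhere, and what each reaches:

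- **Core screening.** All entrants completed the core study, and the K-SADS-PL was done at its screening (section 7.2.3). It may cover ideation before the core study. As a screening record it cannot cover ideation first reported at a later core visit.
- **Carried-over history.** Footnote a brings forward "medical and psychiatric history from screening in the core study". It has the same time limit, and it is not shown to record item-level answers.
- **Carried-over adverse events** (Table 2, section 11.4.1). These may show ideation reported during the core study, but the documents do not say how such reports were recorded.
- **Exclusion 1.** Covers imminent risk as judged by the investigator.
- **Later C-SSRS.** Visits 2E to 10E give 9 assessments and Visit 13E gives 1, so 9 + 1 = 10, with referral of significant ideation. These detect events after entry.
- **Section 13.1.** Treatment must stop if the investigator judges that the child can no longer safely participate.

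None of these applies the item 4 or 5 rule to a report made at an earlier core visit.

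**The case against.** The strongest reply is that any harm depends on a protocol we cannot see. If the core study excluded lifetime item 4 or 5 ideation, the period before it is already covered. If it withdrew children who reported such ideation during treatment, they are not completers and cannot enter. A careful investigator could also apply the lifetime words regardless of the form. On this view the documents show unclear drafting and no demonstrated enrolment gap. The five between-visit safety contacts (section 11.4.12) and the independent monitoring board (section 12.5) reduce the remaining risk further.

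Much of this stands. A reader might infer that children with past suicidal intent will be enrolled, or that nobody screened for ideation before the core study. The documents support neither inference, because the core criteria and stopping rules are simply not visible.

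What does not stand is the view that only detail is missing. If the lifetime words govern, the named form cannot support them. If the form governs, the lifetime words do nothing. Either way the criterion fails as written, and a site that follows it exactly can miss a report already on file.

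One could instead repair it by deleting the lifetime wording and relying on core screening. That would be coherent, but it narrows the sponsor's stated scope and, on these documents, leaves reports from earlier core visits unaddressed.

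**Conclusion.** The point holds as an internal inconsistency in a safety exclusion. The rule says lifetime, and its only named source is 1 form covering 1 interval. A child with item 4 or 5 ideation reported at an earlier core visit can pass that check although the lifetime words exclude the child.

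The conclusion rests on two assumptions: that the form's recall period is what its title says, and that the core study collected the C-SSRS before Week 6. How many children are affected, if any, cannot be derived.

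A reader might also infer that the safety results would be compromised. They would not be: no endpoint, analysis population or planned summary changes. The case for acting is child safety and consistent application across sites. The correction is worth making because it is cheap, though partial safeguards reduce the practical risk.

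**What to change.** In both the Synopsis and section 8.2, reword exclusion 2 so that it names records able to answer it: exclude any subject with a yes to ideation item 4 or 5 on any C-SSRS completed in the core study, meaning any screening or lifetime form plus every Since Last Visit form through Week 6.

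Add that the investigator should review the carried-over psychiatric history and adverse events for documented suicidal ideation with intent. This should be supporting information and not an item-level rule, since those records are not shown to capture answers to items 4 and 5. If the core study used no lifetime form, this review is what remains for ideation older than the core C-SSRS records reach.

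The cost is a wording change in two places and a short review of existing records at OL Baseline. No new visit or procedure is needed. A few more children may be excluded; the number cannot be derived from the documents.

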## 9. STUDY DRUG MATERIALS AND MANAGEMENT

## 9.1. Description of Study Drug

The study medication is described in Table 5.

**Table 5:** Investigational Product

Attribute	Study Medication		
Product name	Dasotraline 2 mg	Dasotraline 4 mg	Dasotraline 6 mg
Dosage form	capsules	capsules	capsules
Unit dose	capsule	capsule	capsule
Route of administration	oral	oral	oral
Physical description	Swedish orange, size #4	Swedish orange, size #4	Swedish orange, size #4

In addition to dasotraline, the active ingredient, each capsule contains: Mannitol United States Pharmacopeia (USP), Sodium Starch Glycolate NF, Talc USP, and Magnesium Stearate NF.

# 9.2. Study Drug Packaging and Labeling

## 9.2.1. Package Description

Study drug will be provided in 1 week blister cards containing 10 capsules of dasotraline 2 mg, 4 mg, or 6 mg capsules (7 days + 3 extra days).

## 9.2.2. Labeling Description

All packaging for the study medications will be labeled with:

- Protocol number
- Sponsor's name and address
- Content (eg number of capsules)
- Investigational New Drug statement
- Instructions for use and storage
- Blank space for subject number (if needed)
- Batch number
- Blank space to record visit number identifier
- Unique medication number (if needed)

## 9.3. Study Drug Storage

All study medication should be stored at United States Pharmacopeia (USP) Controlled Room Temperature: 20°C - 25°C (68°F - 77°F); excursions permitted to 15°C - 30°C (59°F - 86°F). The subject's parent/legal guardian will be instructed to store the study medication at room temperature.

In addition, the subject's parent/legal guardian will be instructed to store the study medication in a location where it cannot be inadvertently accessed and consumed by the subject and to remove all previous ADHD treatments from the subject's access.

# 9.4. Dispensing of Study Drug

An Interactive Response System (IXRS) will be used to manage subject enrollment. The IXRS is an integrated web based subject and drug management system.

The IXRS will be used to assign subject numbers that will be linked via IXRS to the subject's previous core study subject number.

Study medication blister cards will be assigned by the IXRS based on the treatment schedule determined by the investigator. The IXRS will generate instructions on which medication number to assign to a subject. Each subject will be dispensed one to four 10-day blister cards per scheduled visit, based on the expected next visit date.

Under supervision from the subject's parent/legal guardian, subjects will self-administer the study drug daily on an outpatient basis (see Section 10.1). The daily dosage will be clearly labeled on the study drug blister card.

